### 14.3.2 Exploratory Objectives

- To examine the correlation of E-selectin ligand expression of leukemic blasts with clinical outcome.
- To examine the correlation of plasma soluble E-selectin concentrations with clinical outcomes.
- To examine the correlation of MRD after induction and consolidation chemotherapy with clinical outcomes.
- To examine the correlation of E-selectin ligand-forming glycosylation genes of leukemic blasts with clinical outcome.

### 14.3.3 Methods

E-selectin ligand will be measured on bone marrow blasts using multiparameter flow cytometry using a standardized panel of monoclonal antibodies designed to identify the blast population. The percentage of cells and mean fluorescence intensity will be used to quantify the extent of E-selectin ligand in this population.

sE-Selectin will be measured from plasma samples obtained at baseline and after induction using a commercially available enzyme-linked immunosorbent assay (ELISA) to human E-selectin.

Expression levels of the E-selectin ligand-forming glycosylation genes, Fucosyltransferase 7 (FUT7) and ST3 Beta-Galactoside Alpha-2,3-Sialyltransferase 4 (ST3GAL4), in RNA extracted from residual bone marrow aspirates of patients diagnosed with AML will be determined by reverse transcription quantitative PCR (RT-qPCR).

To determine whether the E-selectin ligand expression is associated with clinical outcomes, descriptive statistics (i.e. mean, median, standard deviation, and range) and graphical methods (i.e. boxplots, jitter plots) will be used to summarize both pre- and post-treatment E-selectin level to understand its distribution in each treatment arm. To evaluate its association to clinical outcomes, two-sample t-tests or Wilcoxon rank-sum tests will be conducted to compare the E-selectin level between those who achieve remission versus not.

Suppose 80% of patients (n=536) enrolled will have a bone marrow sample available for E-selectin analysis. Assuming 375 patients (out of 536 patients) achieving a remission, we will have 88% power to detect an effect size of 0.3 (effect size defined as the difference in mean divided by the standard deviation,  $\delta = |\mu_1 - \mu_2|/\sigma$ ) in baseline E-selectin expression levels between the responders and non-responders at the 0.05 two-sided alpha level; this assumes a remission rate of 70%. Furthermore, to analyze multiple factors related to the probability of achieving CR, logistic regression models will be constructed. For DFS, EFS, and OS, E-selectin level along with other potentially prognostic factors will be examined in multivariable analyses, using Cox regression model, stratified by treatment arm. Similar analyses will be conducted for sE-selectin. Secondary analysis will evaluate the sE-selectin expression level pre- vs. post-induction will be compared using two-sample t-tests or Wilcoxon rank-sum tests, as well as descriptive statistics and graphical methods. Exploratory analysis will be conducted to investigate the optimal cut-point of baseline E-selectin expression level through ROC analysis.

Flow cytometry will be used to assess for MRD by discriminating between normal regenerating hematopoietic cells in the bone marrow and any remaining acute myeloid leukemia (AML) which abnormally expresses cell surface antigens [27]. This technique, termed “Difference from Normal” is based on correlating the quantitative expression of multiple cell surface antigens (gene products) in the specimens using standardized antibody panels. The Difference from Normal approach identifies all the normal regenerating cells within the specimen first, subtracts them away and then detects clusters of abnormal cells within the remaining data set. Using this technique, it is possible to define the precise composition of the specimen, identifying cells of all lineages and maturational stages as well as assessing specimen quality in addition to detecting and quantifying any abnormal cell population [28].

Bone marrow specimens will be obtained at the end of induction and the end of consolidation. The quality of each specimen will be defined based on total cellularity, hemodilution, and viability. Collection of fewer than 100,000 cells in each of 8 tubes, significant hemodilution of >50%, lymphoid predominance of >50%, or significant cell death resulted in a specimen quality classification of suboptimal or inadequate [29].

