## 14.3 E-selectin studies (Alliance A041701-LC1)

### 14.3.1 Background

E-selectin mediated interactions may play a role in AML and the expression of E-selectin or its binding epitope (sialyl  $Le^{a/x}$ ) may predict the clinical course and patient outcomes in AML. Increased expression of E-selectin, as seen in inflammatory conditions, malignant states such as leukemia, and during chemotherapy, is also associated with increased shedding of E-selectin from the cell surface resulting in higher levels of sE-selectin in the circulation.

We will measure the levels of E-selectin ligand on pretreatment bone marrow blasts in patients treated with or without uproleselan to describe the cell-surface expression pattern of E-selectin ligand on AML blasts and to determine the effect on clinical outcomes. We will also examine plasma sE-selectin at baseline and after treatment with chemotherapy with or without uproleselan to determine if E-selectin inhibition affects sE-selectin levels and to correlate plasma levels with clinical outcomes.

E-selectin (E-sel) is a cell adhesion glycoprotein that is expressed on endothelial cells and has been implicated in therapeutic resistance. In most myeloid leukemias, leukemic blasts express E-selectin ligands, which contain the glycan epitope of the carbohydrate sialyl  $Le^x$  ( $sLe^x$ ). This sequestration in the bone marrow vascular niche, leading to cell adhesion-mediated drug resistance and resultant poor clinical outcome. Uproleselan is an E-selectin antagonist which interrupts leukemic cell homing to the vascular niche, increases susceptibility to cytotoxic and targeted therapies and can be a potent adjunct to therapeutics. In deed data has demonstrated a correlation between leukemic cell surface

levels of E-selectin ligands using multiparameter flow cytometry and response to uproleselan.

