Recently, transcriptome profiling of E-selectin ligand-forming glycosylation genes have been explored from public data sets to identify elevated E-selectin ligand expression in patients with AML. RNA-seq data from patients treated in COG AAML1031 ( $N = 1,074$ ) was available for evaluation. Of 24 genes examined, Fucosyltransferase 7 (FUT7) and ST3 beta-galactoside alpha-2,3-sialyltransferase 4 (ST3GAL4) were significantly associated with adverse outcome ( $HR = 1.013, p < 0.0001$ , and  $HR = 1.023, p < 0.0001$ , respectively), and directly synthesize sLex. Patients highly expressing *FUT7* (highest quartile of expression) had significantly worse outcome than lower expressors (lowest 3 quartiles of expression), with a 5-year OS of 50.3% vs. 68.3% ( $p < 0.0001$ ). Similarly, those with high *ST3GAL4* expression had a 5-year OS of 51.3%, compared to 68.1% for low expressors ( $p < 0.0001$ ). High expression of these genes was shown to be associated with cell surface E-selectin ligand expression. Taken together these data suggest a strong correlation between transcriptome measurements of E-selectin ligand-forming glycosylation genes and cell surface glycosylation levels of E-selectin ligands, and lend support for the use of E-selectin ligand glycosylation genes as predictive biomarkers.

We will measure the expression of E-selectin ligand-forming glycosylation genes from pretreatment bone marrow blasts treated with or without uproleselan to describe the RNA expression levels of these genes on AML blasts and to determine the effect on clinical outcomes.

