#### 14.3.4 Statistical Analysis Plan

A041701 is a randomized Phase II/III study. The study will open with accrual open to two arms (one experimental arm and one control arm). The total Phase II sample size is

expected to be approximately 262 eligible patients (131 patients per arm). The total Phase III sample size is expected to be 670 (335 patients per arm). In the event that the Alliance Data Safety and Monitoring Board (DSMB) releases the requested Phase II data, the hypothesis-generating analyses described here will be performed based on Phase II accrual. Otherwise, this proposal is mainly based on Phase III accrual. Because this substudy is being newly incorporated in a protocol amendment post-study activation (54 patients accrued as of 11/22/2019), the current accrual rate suggests that approximately 600 evaluable Phase III patients may participate in this substudy.

We assume that 60% patients treated on A041701 will achieve a CR/CRi. Of those achieving CR/CRi, we expect to have end-of-induction marrow samples for MRD assessment on 90% of patients (n=324), and blood samples on 95% of patients (n=342).

We note that the Cox regression models below will be stratified by treatment arm as appropriate. Multivariable analyses will be evaluated as a complement to each univariate analysis. Multivariable analyses will include baseline covariates age, gender, performance status, cytogenetic risk, white blood cell count, platelet count, bone marrow blast percentage, and number of induction courses (1 vs 2).

*1. Primary integrated objective (To evaluate whether the presence of MRD will be a strong predictor of relapse-free survival (RFS) in patients achieving a CR/CRi following induction chemotherapy):*

We expect that approximately 25% of patients who achieve a CR/CRi will have detectable MRD by flow cytometry using the current methodology. Log-rank test will be used to assess associations between MRD and RFS. And RFS will be estimated by the Kaplan-Meier method.

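### E-selectin substudy (LC1): the background argues for predictive markers, but no treatment-by-marker term is planned, so a predictive marker cannot be told from a prognostic one

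*Combined protocol and SAP*

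**What the plan says.** **Rationale (section 14.3.1).** For the cell-surface ligand, the protocol cites data correlating leukemic cell surface "levels of E-selectin ligands using multiparameter flow cytometry and response to uproleselan". For FUT7 and ST3GAL4, it concludes that the data "lend support for the use of E-selectin ligand glycosylation genes as predictive biomarkers". It proposes to measure the markers in patients treated with and without uproleselan.

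**Objectives (section 14.3.2).** They are headed exploratory. The one for the ligand reads "To examine the correlation of E-selectin ligand expression of leukemic blasts with clinical outcome". Those for soluble E-selectin and the two genes are framed the same way.

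**Analysis (section 14.3.3).**
- E-selectin level is compared between patients who do and do not reach remission, by t-test or Wilcoxon test.
- For remission the plan adds that "to analyze multiple factors related to the probability of achieving CR, logistic regression models will be constructed", naming neither an arm term nor an arm-by-marker term.
- DFS, EFS and OS are examined in multivariable analyses "using Cox regression model, stratified by treatment arm".
- "Similar analyses will be conducted for sE-selectin".
- For FUT7 and ST3GAL4 the section describes the RT-qPCR measurement but writes no outcome model.

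**Elsewhere.** The only interaction model in section 14.3 is between blood and marrow MRD (section 14.3.4). Section 13.2.5 plans treatment hazard ratios within subgroups of baseline prognostic factors. It does not name E-selectin and plans no interaction test.

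**The concern.** A prognostic marker is associated with outcome whatever the treatment. A predictive marker changes the size of the treatment effect. A randomised control arm is what allows the two to be separated, and this trial has one. The background claims a link with response to uproleselan, yet every E-selectin analysis written down estimates a single marker effect shared by both arms.

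Two misreadings could follow. A pooled association could be cited as support for choosing patients for uproleselan when it says nothing about benefit from the drug. Conversely, a marker whose effects run in opposite directions in the two arms could average to nothing and be dismissed. The plan also searches for an optimal cut-point of baseline expression by ROC analysis. With no arm-specific step, that cut-point could be mistaken for a treatment-selection threshold.

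**Working it through.** **1. The plan's own power figure.** Section 14.3.3 gives 375 responders of 536 (so 161 non-responders), an effect of 0.3 SD, two-sided alpha 0.05 and 88% power. The standard error of the difference is √(1/375 + 1/161) = 0.0942 SD, so 0.3/0.0942 = 3.18 and power = Φ(3.18 − 1.96) = 88.9%. The figure reproduces, but it is power for a marker-remission association pooled over arms. It also presumes 80% of 670 patients, and Amendment 04 ended accrual. With about 200 Phase II substudy patients (section 14.3.4) and the same 70% remission rate, 140 versus 60, power for 0.3 SD is about 49%.

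**2. What the arm-stratified model can see.** Simulation used 500 runs per setting with 200 patients allocated 1:1. Control median EFS was 7 months and the treatment HR 0.64 (both section 13.1.2). Assumptions were exponential times, a standard normal marker, uniform censoring at 12-42 months and no other covariates. Runs averaged about 168 events. HRs are per SD of the marker.

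| True marker HR (control / experimental) | Planned model: HR, rejection | With arm-by-marker term: interaction HR, rejection |
|---|---|---|
| 1.25 / 1.25 (prognostic only) | 1.27, 84% | 1.00, 7% |
| 1.56 / 1.00 (predictive) | 1.26, 81% | 0.64, 79% |
| 1.25 / 0.80 (opposite directions) | 1.02, 7% | 0.64, 79% |

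The planned coefficient tracks the average of the two arms' log hazard ratios: √(1.5625 × 1.00) = 1.25 in the second row and √(1.25 × 0.80) = 1.00 in the third. The first two rows cannot be told apart by that coefficient. The added term was fitted inside an arm-stratified Cox model and recovered the interaction.

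**3. Precision available now.**
- Sampled patients (assumption): 80% of 200 = 160, to 80% of 262 = 210. The 80% is the plan's own sampling fraction.
- EFS events: 191/262 = 0.729 (sections 13.2.1 and 13.1.2), giving 0.729 × 160 = 117 to 0.729 × 210 = 153.
- Median split, 1:1 allocation, events spread evenly over four cells: SE of the log ratio of HRs = √(16/D). This is √(16/117) = 0.370 and √(16/153) = 0.323.
- 95% CI factor either way: exp(1.96 × SE) = 2.07 and 1.88.
- Ratio of HRs for 80% power: exp(2.80 × SE) = 2.82 and 2.47.

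**4. Continuous marker.** Here SE per SD = √(4/D). The documents give no interaction effect size, so a range is assumed. With 0.729 × 200 = 146 events, two-sided 0.05:

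| Interaction HR per SD | Power at 146 events | Events for 80% power |
|---|---|---|
| 0.60 | 87% | 121 |
| 0.70 | 58% | 247 |
| 0.75 | 41% | 380 |
| 0.80 | 27% | 631 |

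Per-SD and median-split ratios are on different scales and should not be compared directly. No OS calculation is shown because the documents give no expected number of deaths for the closed population.

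**The case against.** The strongest reply is that nothing declared is missed. The objectives are exploratory and ask for correlation with outcome, and the planned tests answer that. This stands: a reader might infer that the substudy fails its own objective, and section 14.3.2 does not support that.

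The rationale is also not wholly predictive. Section 14.3.1 opens with markers that may foretell the course of AML in general. The gene evidence it cites is survival by expression level, with no comparison by uproleselan treatment, so its use of the word predictive may be loose. This stands in part. The sentence on the ligand is a treatment-response claim, and the wording for the genes invites the same reading.

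Three further inferences are tempting and should be resisted.
- That stratifying by arm is the fault. It is not, because an arm-by-marker term fits within an arm-stratified model.
- That the planned model gives the same answer whether or not the marker is predictive. It does so only when the arm averages coincide; the third simulated case gave a different answer.
- That the stratification statement in section 14.3.4 is further evidence. It governs the MRD models that follow it.

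Section 13.2.5 could be read as covering baseline E-selectin, since section 14.3.3 groups it with other prognostic factors. That would give descriptive treatment hazard ratios by marker level, but the marker is not named and no interaction would be estimated.

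Finally, no section plans to select patients on these markers, and the Phase II-based analyses are labelled hypothesis-generating. The harm is therefore one of interpretation, and the yield of an interaction analysis is modest.

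**Conclusion.** The point holds as a mismatch between rationale and analysis. The background raises a treatment-response question for the ligand and labels two genes predictive. The written analyses estimate only an association pooled over arms, and for the genes no outcome model exists. The missing treatment-by-marker term is the whole of the fault.

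An interaction estimate would be imprecise but informative for large effects only. A median split gives an interval of roughly a factor of two either way. A continuous marker has good power only for an interaction near 0.60 per SD. These sizes rest on the assumed number of sampled patients, on reaching 191 EFS events (section 13.2.1 allows the decision to proceed with fewer), on 1:1 balance among sampled patients, and on proportional hazards.

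**What to change.** For each baseline marker (ligand, soluble E-selectin, FUT7, ST3GAL4), in all randomised patients with a baseline sample, add an exploratory model containing treatment, the marker (continuous, log scale) and their interaction:
- Cox models for EFS and OS, with the randomisation factors (age group, performance status, de novo versus secondary or therapy-related disease) as strata;
- a logistic model for CR/CRi.

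Report arm-specific marker effects and the interaction, each with a 95% CI. Keep the arm-stratified Cox model as the prognostic analysis, and write it out for the two genes. Leave DFS there too: it starts at remission, after randomisation, so its arms are no longer a randomised comparison.

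State the plan before the EFS and OS data are released (section 13.5). Label the results hypothesis-generating, since four markers by three outcomes gives 12 interaction estimates at low power. The cost is one model per marker and outcome, using baseline samples already specified in section 6.2. If the study team does not want this analysis, the alternative is to reword section 14.3.1 so that the markers are presented as prognostic only.

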#### 6.2 Specimen collection and submission

The Alliance A041701 Correlative Science Manual (CSM) contains instructions for specimen collection, processing and shipping. The manual can be found on the BioMS and CTSU websites. Questions regarding the CSM should be addressed to the contacts specified in the manual.

For all patients registered to Alliance A041701: Bone marrow and peripheral blood will be collected and banked for molecular genetic analysis described in [Section 14.2](#).

For patients registered to substudy A041701-LC1 and/or patients who consent to banking: All participating institutions must ask patients for their consent to participate in Alliance A041701-LC1 and the banking of their specimens for future studies, although patient participation is optional. Rationale and methods for the scientific components of these studies are described in Section 14.0. For patients who consent to participate, bone marrow and blood samples will be collected at the following time points for these studies:

	At Pre-registration	End of Induction	End of Consolidation	Relapse	Storage/Shipping conditions	Submit to:
For all patients registered to A041701, submit the following						
Bone marrow aspirate (EDTA/lavender top)	5 mL				Ambient	HEME
Peripheral blood (EDTA/lavender top)	10 mL				Ambient	HEME
For patients registered to A041701-LC1A, submit the following						
Bone marrow aspirate (heparin/green top)	2 mL	2 mL	2 mL		Ambient	Hematologics
Peripheral blood (Na citrate/light blue top)	2.7 mL	2.7 mL			Frozen/dry ice	HEME

For patients who consent to banking B , submit the following						
Bone marrow aspirate (EDTA/lavender top)	5 mL	5 mL	5 mL	5 mL	Ambient	HEME
Peripheral blood (EDTA/lavender top)	10 mL	10 mL	10 mL	10 mL	Ambient	HEME

- 1 Or submit 30 mL peripheral blood (EDTA/lavender top) if marrow inaspirable or if the patient has had a bone marrow aspiration prior to pre-registration and refuses to have another one performed. This peripheral blood is in addition to the 10 mL required prior to treatment.

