#### Phase II component

**Final analysis:** The Phase II decision-making will be conducted when at least 191 events are observed (approximately expected 37 months after the first patient enrolled). If less than 191 events are observed 2 years after Phase II accrual ends, then the Phase II decision will occur at the target data lock.

At the final analysis of the Phase II, it will be concluded that the experimental arm regimen is promising, if we a one-sided p-value  $< 0.10$  from the log-rank test favoring the experimental arm.

*As of Amendment 04, there will be no additional accrual to the Phase III component of the trial regardless of the outcome of the Phase II analysis. Given the maturity of follow-up on the current patients and no additional accrual to the trial, the final Phase III OS analysis will also be performed at the time of final Phase II EFS analysis. All Phase III alpha (one-sided 2.5%) will be spent at this analysis. The target data lock date is August 12, 2024.*

**Interim analysis:** We will conduct a futility interim analysis which will take place after 50% of the total events have occurred (approximately 25 months after the first patient enrolled). If at the planned interim analysis the hazard ratio is  $>1.0$  in favor of the control arm, the recommendation will be to stop further accrual to the experimental arm and conclude that the novel regimen does not have improved EFS.

We will suspend accrual between phase II and III. In order to protect the phase III comparison, the results of the phase II portion will only be released to the FDA and/or industry sponsors for regulatory purposes, contingent upon the approval and recommendation from the Alliance Data Monitoring Committee. Other than that, the Alliance DMC will only release whether the criteria for continuation to Phase III have been satisfied and not any of the actual results.

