In the calculations below, the RFS is assumed to follow an exponential distribution with a median of 11.5 months (null hypothesis). For the RFS outcome (assuming 59 months of accrual and an additional one year of follow-up per protocol), the marrow results (n=324) will have 80% power to detect an absolute difference in median RFS of 5 months between MRD- and MRD+ patients (HR = 0.7), 13 months for MRD- versus 8 months for MRD+ with a two-sided alpha of 0.05, and the blood (n=342) results will have 83% power for the same effect size and alpha level. C-statistics will be calculated to quantify the model's ability to predict outcomes. We will also fit multivariable Cox regression models with both end-of-induction MRD (present vs absent) plus the covariates listed above.

In the event that the Alliance Data Safety and Monitoring Board (DSMB) releases the requested Phase II data, the hypothesis-generating analyses described here will be performed based on Phase II accrual. Similarly, because this substudy is being newly incorporated in a protocol amendment post-study activation (54 patients accrued as of 11/22/2019), the current accrual rate suggests that approximately 200 evaluable Phase II patients may participate in this substudy.

For the RFS outcome (assuming additional 18 months of accrual and an additional one year of follow-up per protocol), the marrow results (n=108) will have 63% power, and the blood (n=114) results will have 65% power for a HR of 0.6 and two-sided alpha of 0.05. C-statistics will be calculated to quantify the model's ability to predict outcomes. We will also fit multivariable Cox regression models with both end-of-induction MRD (present vs absent) plus the covariates listed above.

*To analyze the association of MRD with overall survival (OS), time-to-relapse (TTR, defined as the time from randomization to relapse, with death without relapse censored at time of death), and relapse risk: OS and TTR will be estimated using the Kaplan-Meier*

method, and compared using log-rank tests. Risk of relapse (RR) will be summarized using cumulative incidence estimates. Cox regression analyses will be used to assess the association between the outcomes of interest and the covariates listed above.

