*To compare whether evaluate whether MRD from the peripheral blood provides similar prognostic information compared to bone marrow:* We will fit multivariate marginal Cox regression models (Wei, Lin, Weissfeld 1989) including either blood and marrow MRD results with covariates for sample type (blood versus marrow), and a second model both blood and marrow MRD, and a third model with the interaction between the two covariates. We will calculate C-statistics for each of these models.

*To compare the presence of MRD at the end of induction versus end of consolidation time points to determine if either of these better predicts RFS:* We will fit multivariate marginal Cox regression models (Wei, Lin, Weissfeld 1989) including either MRD results at the end of induction or at the end of consolidation. We will calculate C-statistics for each of these models.

*To compare the rates of MRD by treatment arm:* Two-way table and chi-square tests will be used to compare the MRD rates by treatment arm.

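### LC1 substudy: an unclear sentence compares pre- and post-induction sE-selectin from the same patients with two-sample tests; state the contrast and, if it is within-patient change, name a paired test

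*Combined protocol and SAP*

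**What the plan says.** Section 14.3.3 (Methods, E-selectin studies) states that "sE-Selectin will be measured from plasma samples obtained at baseline and after induction". In Section 6.2, the LC1 block of the specimen table has a row beginning "Peripheral blood (Na citrate/light blue top" that calls for 2.7 mL at pre-registration and 2.7 mL at end of induction. Each LC1 registrant is therefore meant to supply both values.

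The analysis of those values is given later in 14.3.3: "Secondary analysis will evaluate the sE-selectin expression level pre- vs. post-induction will be compared using two-sample t-tests or Wilcoxon rank-sum tests". Descriptive statistics and graphs are planned alongside.

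Section 14.3.1 gives the purpose of the plasma measurements as "to determine if E-selectin inhibition affects sE-selectin levels and to correlate plasma levels with clinical outcomes". The matching objective in 14.3.2 covers only the second half of that: "To examine the correlation of plasma soluble E-selectin concentrations with clinical outcomes". No power, sample size, standard deviation or correlation is stated for the pre/post comparison.

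**The concern.** A two-sample t-test or rank-sum test treats the two sets of values as coming from different people. Here they come from the same people, so the standard error used is wrong unless the two measurements are uncorrelated. With positive correlation it is too large: the test rejects too rarely under the null and loses power for small shifts. It does not create extra false positives.

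The sentence also does not parse. Two analysts could reasonably read it differently, one testing pre against post and the other testing change between groups, and could choose after seeing the data. At stake is an exploratory result on a pharmacodynamic marker. Accrual is closed, so lost precision cannot be made up with more patients, whereas using the pairing already present in the samples costs nothing.

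**Working it through.** **The plan's own figure.** The only power figure given beside this sentence is 88% for an effect size of 0.3 in baseline E-selectin, 375 responders against 161 non-responders (536 − 375), two-sided 5%. The noncentrality is 0.3 × √(375 × 161 / 536) = 3.18, so power = Φ(3.18 − 1.96) = 89% (88.8% with the t distribution, 87.5% for the rank-sum test under normality). The figure reproduces. It concerns independent groups, for which two-sample tests are correct, and this point does not affect it.

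**Inputs for the pre/post comparison.**
- Pairing: Sections 6.2 and 14.3.3, as above.
- Number of pairs: not stated. Section 14.3.4 projects that "approximately 200 evaluable Phase II patients may participate in this substudy". That projection applies rather than the Phase III figure of about 600, because under Section 13.2.1 "there will be no additional accrual to the Phase III component of the trial". I use 200 pairs, as if every one of those patients had both samples, and 150 and 100 as assumed lower values.
- Correlation rho, size of shift and ratio of post to pre SD (k): not stated, so all are assumptions shown over a range.

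**Formulas** (normal approximation, baseline SD 1, n pairs, shift d):
- SE assumed by the unpaired test: √((1 + k²)/n)
- True SE: √((1 + k² − 2·rho·k)/n)
- True size of the nominal 5% unpaired test: 2 × [1 − Φ(1.96 × assumed SE / true SE)]. With k = 1 this is 2 × [1 − Φ(1.96/√(1 − rho))].
- Unpaired power: Φ((d − 1.96 × assumed SE)/true SE)
- Paired power: Φ(d/true SE − 1.96)

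**Worked case**, n = 200, rho = 0.5, k = 1, d = 0.2. Assumed SE = √(2/200) = 0.100; true SE = √(1/200) = 0.0707. Unpaired power = Φ((0.2 − 0.196)/0.0707) = 52%. Paired power = Φ(0.2/0.0707 − 1.96) = 81%.

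**Results with equal SDs** (power is unpaired v paired):

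| rho | True size, unpaired | 0.2 SD, 200 pairs | 0.2 SD, 150 pairs | 0.2 SD, 100 pairs | 0.3 SD, 200 pairs |
|---|---|---|---|---|---|
| 0 | 5.0% | 52% v 52% | 41% v 41% | 29% v 29% | 85% v 85% |
| 0.3 | 1.9% | 52% v 67% | 39% v 54% | 26% v 39% | 89% v 95% |
| 0.5 | 0.6% | 52% v 81% | 37% v 69% | 22% v 52% | 93% v 99% |
| 0.7 | 0.03% | 53% v 95.5% | 34% v 88.5% | 16% v 73% | 97% v >99% |

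**Sensitivity.** If the post-induction SD is half or double the baseline SD, true size is 2.5%, 1.1% and 0.3% at rho 0.3, 0.5 and 0.7. At rho −0.2 the direction reverses and size is 7.4%. For a 0.5 SD shift at rho 0.5, both tests exceed 98% power even with 100 pairs.

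**Simulation, 200 pairs.** For the t-tests (20,000 runs), unpaired size was 5.2%, 1.9%, 0.6% and 0.04% at rho 0, 0.3, 0.5 and 0.7; power at 0.2 SD and rho 0.5 was 52% v 81%. Rank-sum against signed-rank (4,000 runs) behaved the same way: rank-sum size was 2.0% and 0.8% at rho 0.3 and 0.5, and power at 0.2 SD and rho 0.5 was 49% v 79%.

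**The case against.** The strongest reply is that no wrong test has been shown, only an unclear sentence. Section 14.3.3 has just named the same two tests for patients with and without remission and has said that sE-selectin will be analysed in a similar way. Section 14.3.1 asks a question about E-selectin inhibition, which is a between-arm question. If the intended analysis compares levels or changes between remission groups or arms, two-sample tests are correct.

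This stands in part: the intent cannot be settled from the text, and the claim that text was merged or lost is an inference. But the sentence names neither groups nor a change score. The remission comparison of levels is already carried over to sE-selectin by the line before it, so this sentence must add something, and what it states is pre versus post. No paired method for sE-selectin appears anywhere in 14.3. Either the test does not fit the stated contrast or the contrast is missing, and both call for the same edit.

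The reply is also right that the harm is small. A loss needs both a small true shift and a material positive correlation, and the documents give neither. Descriptive and graphical results would be reported anyway, and change over time is not a listed objective. The figure of about 200 is a projection from accrual in late 2019, not a count of plasma pairs, so the power figures are illustrative.

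**Conclusion.** The point holds at low severity. Read as written, the plan applies tests for independent groups to paired data. For positive rho the test is conservative, with true size 1.9% to 0.03% at rho 0.3 to 0.7. With 200 pairs and a 0.2 SD shift, it gives up about 15 to 43 percentage points of power over that range (67% − 52% to 95.5% − 53%). At rho 0 there is no loss, and for large shifts the loss is negligible. These sizes rest on assumed correlation, shift, SD ratio and number of pairs. What does not rest on assumption is that the sentence is unclear, that both samples come from the same patients, and that no paired method is named.

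**What to change.** Rewrite the sentence so that it names one contrast and the test that fits it.

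- If within-patient change is meant: specify a paired t-test or Wilcoxon signed-rank test in patients with both samples, fix the measurement scale in advance, and report the number of incomplete pairs by arm.
- If change between groups is meant: name the groups and define the change score; the two-sample tests can then stay.

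This costs one sentence of analysis text, with no new samples or assays. Patients with only one sample drop out of a paired test, which is why their number should be reported.

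Optional: the question in 14.3.1 about the effect of E-selectin inhibition has no between-arm test for sE-selectin; 14.3.4 provides one only for MRD ("Two-way table and chi-square tests will be used to compare the MRD rates by treatment arm"). A baseline-adjusted comparison (ANCOVA) could be added, labelled exploratory and limited to patients sampled after induction, who are a post-randomization subset. With an assumed 100 per arm, SE = √(2(1 − rho²)/100), which gives power of 29% to 51% for 0.2 SD and 56% to 84% for 0.3 SD over rho 0 to 0.7. It would add one sentence and one exploratory test. Since 14.3.2 does not list this question as an objective, description by arm alone is also defensible.
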